14.0 ADVERSE EVENT REPORTING

14.1 Adverse Event Definitions

14.1.1 Adverse Events

Any unfavorable or unintended sign, symptom, or illness that develops or worsens during the course of the study (treatment and follow-up) regardless of causality. This includes abnormal clinical or laboratory findings.

14.1.2 Unanticipated Adverse Events

Any serious adverse effect on health or safety or any life-threatening problem or death caused by, or associated with, a device, if that effect, problem, or death was not previously identified in nature, severity, or degree of incidence in the investigational plan or application (including a supplementary plan or application), or any other unanticipated serious problem associated with a device that relates to the rights, safety, or welfare of subjects [21 CFR 812.3(s)].

Please note: The CHR (UCSF IRB) uses the term ‘Unexpected’ Adverse Events, which includes unanticipated events that are not necessarily serious or life-threatening.

14.1.3 Serious Adverse Events

A serious adverse event (SAE) is one that results in any of the following outcomes regardless of dose:

- Death
- Life-threatening (places the subject, in the view of the investigator, at immediate risk of death from the reaction as it occurred), including hepatic decompensation requiring hospitalization or expedited liver transplantation
- Inpatient hospitalization or prolongs existing hospitalization,
- Persistent or significant disability/incapacity (a substantial disruption of a person’s ability to conduct normal life functions),
- Birth defect/congenital anomaly,
- Any important medical event that may not result in prior listed outcomes but, based upon appropriate medical judgment, may jeopardize the subject, and may require medical or surgical intervention to prevent one of the prior listed outcomes.

An adverse event is not considered serious if it does not satisfy at least one of these criteria.

14.1.4 Laboratory Adverse Events

Laboratory test value abnormalities are recorded as adverse events (AE) if they are designated as clinically relevant (defined as any abnormality which requires treatment, causes symptoms, places the patient at risk for morbidity, and/or causes premature withdrawal from study) and represent a change of ≥ 1 grade from baseline. Laboratory abnormalities will not be considered clinically-relevant adverse events if they do not satisfy at least one of these criteria.

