1.2 TACE Toxicity

Complication rates following TACE are high (25-45%) with the majority being reversible elevations of hepatic transaminases and serum bilirubin without an impact on long-term prognosis, however, for a small proportion of patients, irreversible hepatic decompensation occurs (15). TACE-related irreversible hepatic decompensation is described as significant and acute elevation of liver function tests, evidence of new ascites, new encephalopathy, or worsening of either. These serious complications, frequently accompanied by deterioration in clinical status, may lead to the requirement of urgent liver transplantation in eligible patients, ineligibility for and/or risk of increased toxicity from systemic therapy with sorafenib or investigational systemic therapies for HCC, or death (16). Rates of complications following conventional TACE performed for patients with marginal hepatic reserve or portal vein thrombosis have been described (16-23).

We have recently completed a retrospective record review of 252 patients with HCC and hepatic dysfunction who underwent 446 cTACE procedures at our institution between 2005 and 2009 (24). Patients were eligible for inclusion if they had one of the following criteria: pre-TACE

bilirubin ≥ 2 mg/dL, aspartate aminotransferase (AST) or alanine aminotransferase (ALT) > 5 times upper normal limit, international normalized ratio (INR) > 1.5 , creatinine > 1.2 mg/dL, platelet count $\leq 60,000/\mu\text{L}$, Model for End-Stage Liver Disease (MELD) score > 15 , Childs-Pugh class B or C, ascites, or portal venous thrombus. Hepatotoxicity was defined as one of the following: new or worsening ascites, encephalopathy, or NCI Common Terminology Criteria for Adverse Events grade 3 or 4 toxicity of bilirubin, AST, ALT, creatinine or INR. Rate and risk factors for persistent hepatotoxicity were determined using generalized estimating equation analysis.

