Reversible hepatotoxicity developed after 90 TACE procedures (20%) in 78 patients (31%). Reversible abnormalities resolved in under 30 days after 63 procedures, in 1-3 months after 19 procedures, and in 3-6 months after 6 procedures. Irreversible hepatotoxicity developed after 41 procedures (9%) in 37 patients (15%). Six patients (2%) received urgent liver transplants, and five (2%) died within 30 days of TACE. Patients at increased risk for procedure-related mortality or urgent need for a liver transplant had baseline elevated serum bilirubin ($p < 0.0001$), elevated INR ($p < 0.0001$), hypoalbuminemia ($p = 0.002$), thrombocytopenia ($p = 0.011$), elevated serum creatinine ($p < 0.0001$), large ascites ($p = 0.0002$), encephalopathy ($p = 0.0002$), or MELD > 15 ($p = 0.0005$).

PRECISION V trial (14) showed that DEB-TACE was better tolerated than cTACE and led to better radiographic responses in patients with more advanced liver disease than cTACE. On the basis of this observation, DEB-TACE may, in fact be the preferred modality for treating patients with hepatic dysfunction. All studies performed on safety of DEB-TACE to date included patients with serum bilirubin < 3 mg/dL, and AST and ALT levels under 5X upper normal limit (14, 26-52). Patients with baseline liver dysfunction at bilirubin and transaminase levels above those included in trials are routinely treated in clinical practice. However, there have been no published studies to date to support safety and efficacy of DEB-TACE in patients with marginal hepatic reserve. A total of 37 patients with hepatic dysfunction (who met the inclusion criteria proposed for this study) have been treated between at UCSF between 2011 and 2013. Their records were retrospectively reviewed. Preliminary results on adverse events following DEB-TACE are summarized in Table 1. No treatment-related deaths and no events hepatic decompensation requiring an urgent liver transplant were encountered in this patient cohort.

Table 1. Severe hepatic and renal adverse events in 37 patients with marginal hepatic reserve who underwent DEB-TACE at UCSF.

Toxicity	Bilirubin N (%)	AST N (%)	ALT N (%)	INR N (%)	Creatinine N (%)
Reversible* grade 3	9 (24)	5 (14)	1 (2.7)	0 (0)	0 (0)
Reversible* grade 4	1 (2.7)	1 (2.7)	0 (0)	N/A	0 (0)
Irreversible** grade 3	0 (0)	0 (0)	0 (0)	0 (0)	0 (0)
Irreversible** grade 4	0 (0)	0 (0)	0 (0)	N/A	0 (0)

*Abnormality returned to baseline within 6 weeks of DEB-TACE

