12.3 Analysis Plan

Demographics and Baseline Characteristics

Demographic and baseline laboratory results will be summarized using descriptive statistics.

Safety Analysis

Patients will be monitored for development of recognized complications of DEB-TACE including liver dysfunction, renal dysfunction, ascites, hepatic encephalopathy, hepatorenal syndrome, biliary injury (stricture or leak), cholangitis, cholecystitis, hepatic abscess, abdominal pain, nausea, vomiting, fatigue, and fever. Adverse events will be graded according to NCI CTCAE version 4.03. Prevalence of adverse events will be summarized using descriptive statistics.

Efficacy Analyses

Analyses will be performed using the intent to treat population with exceptions as defined below, which require patient replacement.

Primary efficacy analysis

Primary efficacy will be evaluated as 1-month radiographic response after last DEB-TACE procedure in treated HCC lesions according to 1) RECIST version 1.1 and 2) mRECIST. Patients who do not have any post-baseline tumor assessments will be counted as non-responders. Point estimates of response rate and confidence intervals will be provided.

Secondary efficacy analyses

1. Overall radiographic response by 1) RECIST 1.1 and 2) mRECIST 6 months after the date of the first planned DEB-TACE procedure. This analysis will take into account all measurable hepatic HCC lesions present on cross-sectional imaging 6 months after the date of the first planned DEB-TACE procedure.
2. Time to untreatable progression (TTUP). TTUP is defined as time to disease progression untreatable by liver-directed percutaneous or surgical methods as assessed by treating investigator(s). Patient follow-up up to 1 year after last DEB-TACE will be allowed for this outcome variable.
3. Time to progression (TTP). TTP is defined as the time interval between date of first DEB-TACE procedure and date of imaging documenting development of intra- or extrahepatic disease progression by 1) RECIST 1.1 and 2) mRECIST. Patient follow-up up to 1 year after last DEB-TACE will be allowed for this outcome variable.

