14.2 Adverse Event Grading

All AEs will be graded according to the NCI Common Terminology Criteria for Adverse Events (CTCAE) version 4.03.

Severity of AEs will be graded using the following general definitions of the CTCAE v4.03 :

- Grade 1 – Mild (no limitations)
- Grade 2 – Moderate (some limitations)
- Grade 3 – Severe (requires medical attention; usual activities stop)
- Grade 4 – Life-threatening/disabling (requires immediate medical help)
- Grade 5 - Death

Causality of AEs will be graded by the treating investigator with review by the Study Chair as follows:

- Unrelated
- Unlikely related
- Possibly related
- Probably related

- Definitely related

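### Laboratory adverse events pass a clinical-relevance filter and Section 12.3 plans no laboratory grade table, so liver and renal laboratory toxicity may be understated and not like-for-like with the cTACE review

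*Combined protocol and SAP*

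**What the plan says.** Section 2.0 makes safety a primary objective, and Section 9.1 rests the safety assessment partly on laboratory tests. Section 14.1.1 includes abnormal laboratory findings among adverse events, but Section 14.1.4 narrows this. It says "Laboratory test value abnormalities are recorded as adverse events (AE) if they are designated as clinically relevant", and defines relevance as any abnormality that "requires treatment, causes symptoms, places the patient at risk for morbidity, and/or causes premature withdrawal from study". Joined to this by *and*, the abnormality must "represent a change of ≥ 1 grade from baseline". The section closes: "Laboratory abnormalities will not be considered clinically-relevant adverse events if they do not satisfy at least one of these criteria".

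Under Safety Analysis, Section 12.3 plans only this for the results: "Prevalence of adverse events will be summarized using descriptive statistics". The laboratory results it summarises in their own right are the baseline ones. Section 13.5.3 enters all grade 3–5 adverse events in the database. A value that was never designated an adverse event falls outside that instruction.

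Section 1.2 describes two historical cohorts from the same institution. In the 252-patient cTACE review, hepatotoxicity meant new or worsening ascites, encephalopathy, or "grade 3 or 4 toxicity of bilirubin, AST, ALT, creatinine or INR". Table 1 of that section is titled "Severe hepatic and renal adverse events in 37 patients with marginal hepatic reserve" and counts events by analyte and grade.

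**The concern.** The filter has a judgement in it, and nothing downstream recovers what the judgement removes. A short-lived, untreated, asymptomatic grade 3 bilirubin or AST rise could be judged not clinically relevant. It would then appear neither as an adverse event nor in any laboratory table.

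The trial is open-label and single-arm. Sections 1.2 and 1.6 justify it by the prospect that DEB-TACE is better tolerated than cTACE, so readers will naturally set its toxicity figures beside the institution's own cTACE review. If one figure has passed a relevance filter and the other has not, a lower rate in the trial could reflect less toxicity or fewer designations, and the report could not tell them apart. Filtering can only remove events, so any bias would favour DEB-TACE.

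**Working it through.** **1. The plan's own figures.** Table 1 of Section 1.2 reproduces: bilirubin grade 3, 9/37 = 24.3% (stated 24); AST grade 3, 5/37 = 13.5% (stated 14); each single event, 1/37 = 2.7%. The Section 10.1.1 benchmarks reproduce too: 20/166 = 12.05% (stated 12%) and 2/166 = 1.20% (stated 1.2%).

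**2. The definitions side by side.**

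| Source | Laboratory event | Relevance filter | Baseline handling |
|---|---|---|---|
| This trial, 14.1.4 | Abnormality designated clinically relevant | Yes, by judgement | At least one grade of change |
| cTACE review, 1.2 | Grade 3 or 4 bilirubin, AST, ALT, creatinine or INR | None stated | Not stated |
| 37-patient DEB-TACE cohort, 1.2 Table 1 | Grade 3 or 4, by analyte | Not stated | Ascertainment rule not stated; reversibility judged against baseline |
| Stopping rules, 10.1.2 | Grade 4 bilirubin; grade 3 or 4 creatinine; not improved within 1 month | None; 14.1.4 not cited | Improvement to baseline or to a lower grade |

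**3. The internal conflict in 14.1.4.** The main sentence requires relevance *and* a one-grade change. If the closing sentence refers to both conditions, meeting either is enough. If it refers only to the four grounds for relevance, there is no conflict, but the text does not say so. Two people could record different events from the same values.

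**4. Illustration of size.** Inputs: grade 3–4 bilirubin in Table 1 = 9 + 1 = 10 of 37, assuming the grade 3 and grade 4 patients are distinct; N = 51 from Section 12.1; *f* = share of such rises designated relevant, which the documents do not give.

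- Rate: 10/37 = 27.0%, Clopper-Pearson 95% CI 13.8–44.1%.
- Expected patients with such a rise: 51 × 10/37 = 13.8.
- Recorded patients = *f* × 13.8:

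| *f* (assumed) | Recorded of 51 | Reported rate |
|---|---|---|
| 0% | 0 | 0% |
| 25% | 3.4 | 6.8% |
| 50% | 6.9 | 13.5% |
| 75% | 10.3 | 20.3% |
| 100% | 13.8 | 27.0% |

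The 27% is itself uncertain. At the confidence limits, the expected number before any filtering is 0.138 × 51 = 7.0 to 0.441 × 51 = 22.5 patients. No renal figure can be given: Table 1 shows no grade 3–4 creatinine events in 37 patients.

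**The case against.** The strongest reply is that a grade 3–4 rise would rarely fail the test. Any one of four grounds is enough, and the ground based on risk of morbidity is broad. Section 14.2 describes grade 3 as "Grade 3 – Severe (requires medical attention; usual activities stop" and grade 4 as life-threatening. Section 10.1.1 itself links irreversible grade 4 hyperbilirubinemia to death or urgent transplant. This stands in part: it makes understatement possible rather than certain. It does not close the gap, because Section 1.2 says that most TACE complications are reversible transaminase and bilirubin rises that do not affect long-term prognosis, and all ten bilirubin events in Table 1 were reversible. Someone could reasonably call such a rise not relevant.

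It can also be said that no formal comparison with the historical cohorts is planned. That is correct: adverse events are summarised descriptively, and the historical rates are used formally only to set stopping rules. The point therefore concerns how the reported rates will be read. It does not affect a planned test.

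Several stronger readings are tempting, and the documents do not support them:

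- *That the historical cohorts counted every grade 3–4 value.* The cTACE review's handling of values abnormal at baseline, and Table 1's counting rule, are not given.
- *That the stopping rules are weakened.* Section 10.1.2 names bilirubin and creatinine grade directly and does not refer to 14.1.4.
- *That the treating investigator decides relevance.* Section 14.1.4 names no decider; Section 14.2 assigns that investigator causality only.
- *That the one-grade requirement is itself a flaw.* In patients who can qualify through abnormal liver tests (Section 4.2), it separates new toxicity from existing disease. Worsening within a grade would not show as a new grade in a grade-based definition either.

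**Conclusion.** The point holds as a reporting weakness in a primary objective. As written, post-baseline laboratory toxicity reaches the results only through a judgement-based filter with internally unclear conditions. The cTACE review's definition, as described, has no such filter. Reported liver and renal laboratory toxicity may be understated, and a comparison with that review may not be like-for-like.

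The size is unknown. The range of 0 to about 14 recorded patients of 51 covers everything from complete loss to no loss. It rests on carrying the 37-patient bilirubin rate over to this trial and on the ten patients being distinct. A reader might infer that toxicity *will* be understated, but the top of the range is no understatement at all, and the documents do not place the trial within it.

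**What to change.** In Section 12.3, Safety Analysis, state that bilirubin, AST, ALT, INR and creatinine are graded by CTCAE version 4.03 from all scheduled laboratory values, whatever their adverse-event designation. Report the worst post-baseline grade and the baseline-to-worst shift per patient. Use these results, not adverse-event counts, for any descriptive comparison with Table 1 of Section 1.2 or the cTACE cohort, and say there that those cohorts' counting rules are not fully stated. In Section 14.1.4, reconcile the *and* in the main sentence with the closing sentence.

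No new tests are needed: Sections 8.4.1 and 8.4.2 already schedule them on days 1, 7, 30, 90, 180, 270 and 360, with days 1 and 7 repeated after each procedure. Because local laboratories are allowed, the reference range should be kept with each value. The cost is one extra table, and the reported toxicity may be higher.

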14.2 Adverse Event Grading

All AEs will be graded according to the NCI Common Terminology Criteria for Adverse Events (CTCAE) version 4.03.

Severity of AEs will be graded using the following general definitions of the CTCAE v4.03 :

- Grade 1 – Mild (no limitations)
- Grade 2 – Moderate (some limitations)
- Grade 3 – Severe (requires medical attention; usual activities stop)
- Grade 4 – Life-threatening/disabling (requires immediate medical help)
- Grade 5 - Death

Causality of AEs will be graded by the treating investigator with review by the Study Chair as follows:

- Unrelated
- Unlikely related
- Possibly related
- Probably related

- Definitely related

14.3 Adverse Event Reporting Period

Reportable AEs are those that occur after treatment begins and up to 1 month after the last DEB-TACE treatment.

Unresolved AEs (Reportable AEs that extend past the 1 month post-treatment period) should continue to be reported on if the condition worsens or results in death.

AEs that occur after the reporting period (first treatment to 1 month post-treatment) are not normally reported unless they are serious AND the investigator or treating physician has reason to believe the event(s) might be related to study participation.

AE reporting will discontinue at time of transplant.

AE reporting will discontinue if patients are taken off study to receive more than four DEB-TACE treatments.

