10.1.1 Rationale

A retrospective analysis of toxicity of conventional TACE method for UCSF patients with HCC and hepatic dysfunction, which included 252 patients and 446 TACE procedures was recently completed (24). This cohort included 166 patients who met the more stringent inclusion criteria for the current study. These patients underwent a total of 260 TACE procedures. In this patient cohort, 20 patients (12%) developed NCI CTCAE grade 4 hepatotoxicity that persisted 1 month following TACE. Of note, patients who had irreversible grade 4 hyperbilirubinemia with or without grade 4 transaminitis had a 27.7% rate of mortality or required an urgent liver transplant within 6 weeks of TACE. This rate was higher than that for patients who had grade 4 transaminitis without grade 4 hyperbilirubinemia, 11.1% of whom died or required an urgent liver transplant within 6 weeks of TACE. These findings suggested that irreversible hyperbilirubinemia was a more robust predictor of mortality or TACE-induced liver failure requiring salvage transplantation than transaminitis.

Based on the same retrospective study (24), a total of 2 patients (1.2%) had grade 4 renal toxicity that persisted 1 month following TACE.

Based on the same retrospective study (24), mortality rate 6 weeks following TACE was 4.8% (8 patients).

No published comparable safety data is available for DEB-TACE with regards to the patient population to be studied. However, a total of 37 patients with marginal liver function (within proposed inclusion criteria for this study) have been treated between 2011 and 2013. Their records were retrospectively reviewed. Preliminary results on adverse events following DEB-TACE are summarized in Table 1. No treatment-related deaths and no events hepatic decompensation requiring an urgent liver transplant were encountered in this patient cohort.

Stopping rules for safety were determined based on the assumption that DEB-TACE may be associated with similar rates of morbidity as conventional TACE.

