10.1.2 Specific Stopping Rules for Safety

Safety data will be routinely monitored and sequential safety assessments will be conducted as subjects are enrolling to the study. The study will be stopped due to safety/toxicity concern prior to interim efficacy analysis if *any* of the following 3 stopping rules are met:

1. Liver dysfunction (clinical or laboratory [total serum bilirubin], grade 4) that does not improve to baseline or \leq grade 3 within 1 month following DEB-TACE in ≥ 7 patients (12% of 51 patients).

OR

2. Renal dysfunction (clinical or laboratory [serum creatinine], grade 3 or 4) that does not improve to baseline or \leq grade 2 within 1 month following DEB-TACE in ≥ 2 patients (1.2% of 51 patients).

OR

3. Any grade 5 AE (death) attributed as at least possibly-related to study intervention in ≥ 3 patients (4.8% of 51 patients).

The stopping rules above were used to generate the following chart, which will be adhered to with regards to stopping enrollment for the reasons of severe toxicity.

Table 4. Number of patients with defined safety/toxicity for the study to be stopped during sequential and continuous safety assessments (based on binomial distribution)

Number patients enrolled in study	3	7	11	13	17	23
Number of patients with grade 4 liver dysfunction, grade 4 renal dysfunction, or study-related death	2	4	6	7	8	9
% chance of stopping enrollment if true SAE rate is $<15\%$	94%	99%	99%	99%	99%	99%
% chance of stopping enrollment if true SAE rate is $<20\%$	90%	97%	99%	99%	99%	97%
% chance of stopping enrollment if true SAE rate is $<30\%$	78%	87%	92%	94%	90%	77%

Note: the study will also be terminated early if any of the 3 stopping rules is observed.

Adverse events grade ≥ 4 will be discussed by the interventional radiologist and medical oncologist and/or hepatologist within 1 business day of being informed of the event. If at any time a patient has a fatal complication at least possibly related to treatment, the study will immediately be put on hold. At that time, the data will be reviewed by a multidisciplinary team as to the etiology. If it is determined that the death was attributed as at least possibly-related to treatment, the study investigators will meet to discuss if the study should continue.

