10. Biochemical response defined as $\geq 50\%$ decrease in alpha-fetoprotein level measured 1 month and 4 months after DEB-TACE.
11. Histopathologic response defined as percentage of tumor necrosis at liver explant histopathology. This will only be explored in the subgroup of patients who undergo a liver transplant. Per UCSF clinical standard, tumor necrosis for HCC lesions is reported as 100%, >90%, 60-90%, 30-59%, and < 30%.

Intention To Treat Exceptions (Patient replacement)

1. Patients who proceed to liver transplant or develop hepatic decompensation between the time of enrollment and the first DEB-TACE treatment will be replaced.
2. Patients who proceed to liver transplant prior to completion of the 1 month safety window after first DEB-TACE will be replaced unless the transplant occurred due to hepatic decompensation or other toxicity attributed as at least possibly-related to protocol therapy, in which case the hepatic decompensation or other toxicity will be deemed a serious adverse event and the patient will be included in safety analysis (see Section 14.1.3).

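### Rule 1 leaves undefined a liver failure transplanted before one month, and Table 4, follow-up, AE reporting and the replacement clause do not agree on it

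*Combined protocol and SAP*

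**What the plan says.** Section 10.1.2 sets three numbered rules. Rule 1 counts "Liver dysfunction (clinical or laboratory [total serum bilirubin], grade 4) that does not improve to baseline" or to grade 3 or lower "within 1 month following DEB-TACE in ≥ 7 patients (12% of 51 patients"). Rule 2 is renal. Rule 3 counts "Any grade 5 AE (death) attributed as at least possibly-related to study intervention in ≥ 3 patients (4.8% of 51 patients"). None of the three names urgent transplant.

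The same section derives Table 4 from these rules and makes it binding. Its event row lists grade 4 liver dysfunction, grade 4 renal dysfunction or study-related death, with no one-month condition. Its last column is 23 patients.

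On what happens at transplant:
- Section 14.3: "AE reporting will discontinue at time of transplant". The same section asks for unresolved events to go on being reported past one month if they worsen or prove fatal.
- Sections 8.4.1, 8.4.2 and 10.3 remove a transplanted patient from the study. Item (e) of the two 8.4 lists adds that SAEs are followed to resolution.
- Section 14.1.3 classes decompensation needing expedited transplant as a life-threatening SAE.
- Section 12.3, second replacement exception: a patient transplanted within a month of the first DEB-TACE is replaced, unless the cause was possibly related toxicity. In that case "the hepatic decompensation or other toxicity will be deemed a serious adverse event and the patient will be included in safety analysis".

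**The concern.** All participants are candidates for liver transplant, so an early transplant is a possible outcome of the toxicity that rule 1 is meant to detect. Section 10.1.1 chose persistent hyperbilirubinemia as the signal because, in the conventional-TACE series, such patients "had a 27.7% rate of mortality or required an urgent liver transplant within 6 weeks of TACE". Rule 1 counts the predictor and rule 3 counts the deaths. The other half of that outcome, salvage transplant, has no place in the rules.

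Four things follow:
1. The rule 1 status of a grade 4 failure transplanted before one month is left to whoever applies the rule.
2. Rule 1 and Table 4 use different definitions of the liver event.
3. A related death after a rescue transplant may fall outside AE reporting and so outside rule 3.
4. The exception in section 12.3 can be read as taking a dosed patient, with any adverse events already seen, out of the safety analysis. Safety is a primary objective.

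A safety boundary should not depend on a reading chosen after the event.

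**Working it through.** **Passages side by side.** Take a patient with possibly related grade 4 liver dysfunction on day 5 who is transplanted on day 14.
- *Rule 1, first reading:* the failure was still grade 4 when the liver was removed, so it did not improve, and it counts.
- *Rule 1, second reading:* reporting closed at transplant and the patient left the study, so failure to improve over one month was never observed, and it does not count. If the SAE is instead followed to resolution and the new liver brings bilirubin to grade 3 or lower within the month, a literal reader could record improvement.
- *Table 4:* the row has no persistence condition, so as worded the event counts on day 5. But the table is said to be generated from the rules, which do have that condition.
- *Which limit is tighter:* for liver events alone, Table 4 allows enrollment to continue until 8 events at 17 patients and 9 at 23. Rule 1 stops at 7. From 17 patients on, rule 1 is the tighter limit, and it is the one with the undefined case. Beyond 23 patients Table 4 gives no limit.
- *Rule 3:* if this patient later dies of a related cause, the transplant sentence in 14.3 has closed AE reporting. The sentence on unresolved events in the same section, and the SAE follow-up sentence in 8.4, point the other way.

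**The plan's own threshold.** Section 10.1.1 gives 20 of 166 patients with grade 4 hepatotoxicity persisting at one month: 20/166 = 12.05%. Then 12% × 51 = 6.12, and the next whole number is 7. The threshold reproduces (7/51 = 13.7%).

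**Effect of not counting early transplants.** Let p be the true rate of qualifying liver events and t the part transplanted before one month and left uncounted. The chance that rule 1 is met in 51 patients is

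P(X ≥ 7) = 1 − Σ (k = 0 to 6) C(51, k) q^k (1 − q)^(51 − k), with q = p − t.

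The plan gives no value for t, so a range is shown. The 2.4-point value is 6/252, from section 1.2: "Six patients (2%) received urgent liver transplants, and five (2%) died within 30 days of TACE".

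| True rate p | All counted | t = 1 point | t = 2.4 points | t = 5 points |
|---|---|---|---|---|
| 12% | 41.4% | 32.7% | 21.6% | 6.4% |
| 15% | 66.0% | 58.4% | 46.8% | 24.5% |
| 20% | 90.8% | 87.6% | 81.8% | 66.0% |

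At 6/252, the expected number of urgent transplants in 51 patients is 51 × 0.0238 = 1.2, and the chance of at least one is 1 − (1 − 0.0238)^51 = 71%.

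**Two limits on these figures.** The local DEB-TACE series in section 1.2 had 0 urgent transplants in 37 patients, so t may be near zero; the exact two-sided 95% upper limit is 1 − 0.025^(1/37) = 9.5%. Also, the table takes 51 patients as the horizon, as the percentages in the rules do. The lead sentence of 10.1.2 speaks of stopping before the interim efficacy analysis. If rule 1 ran only to 17 patients, the chance of 7 events at p = 12% would be 0.23% with all counted and 0.06% at t = 2.4 points, negligible either way.

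**The case against.** The strongest reply is that the text already covers this patient. Rule 1 does not ask for a one-month value from the native liver, and a failure still grade 4 at transplant fits its plain words. Table 4 counts the event when it occurs. The transplant sentence in 14.3 ends later reporting; it does not erase an event reported before transplant. The event is an SAE, goes to the IRB and the monitoring committee, and a grade 4 event is discussed within one business day. Section 10.1.2 also lets the study be held or ended for other recognized complications. Deaths are sought after removal for overall survival (12.3), and section 13.5.3 has all patient deaths reported to the FDA.

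Much of this stands, and it rules out the stronger inference a reader might draw, that a rescued liver failure escapes all three rules. The documents are silent on its classification; they do not exclude it. Three related inferences also fail:
- *That a toxicity transplant after session 2, 3 or 4 drops out of the analysis.* It is not among the listed exceptions, so that patient stays in by default.
- *That most of the worst historical outcomes (6 transplants against 5 deaths) would go uncounted.* The six transplants are not clearly dated, and one done after a month of persisting grade 4 dysfunction would already be counted. The cohort of 252 is also wider than the 166 who met this trial's criteria, for whom no transplant count is given.
- *That bias in the safety set is shown.* Removal is only implied by an exception listed after the efficacy analyses, and the safety paragraph of 12.3 states no exclusion.

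What the reply does not supply is a statement that SAE status, or inclusion in the safety analysis, means counting toward rule 1. The hold for other complications is discretionary. Knowing of a death is not the same as recording it as a related grade 5 event for rule 3.

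**Conclusion.** The point holds as an undefined case in a safety rule together with passages that conflict, at moderate severity. Rule 1 does not determine the status of a possibly related grade 4 liver failure transplanted before one month. Table 4 uses a different liver definition and stops at 23 patients. Section 14.3 conflicts with the SAE follow-up in 8.4, so a related death after transplant could be missed for rule 3. Section 12.3 implies that some dosed patients leave the safety analysis.

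At a true rate of 12%, the choice of reading moves the chance of meeting rule 1 in 51 patients from 41% to 33% if 1 point is affected, or to 22% if 2.4 points are. This assumes that rule 1 runs over all 51 patients, that every early transplant goes uncounted, and, for the larger shift, that the rate from the wider conventional-TACE cohort applies. With 0 of 37 in the local DEB-TACE series, the effect could be close to nil.

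**What to change.** Reconcile sections 10.1.2 (rules and Table 4), 8.4, 10.3, 12.3 and 14.3:
1. Use one liver event definition for rule 1 and Table 4, and say what governs beyond 23 patients.
2. State explicitly how a toxicity-driven transplant before one month, after any DEB-TACE session, is classified for rule 1 and Table 4. The statement should be consistent with the SAE status given in 12.3 and 14.1.3.
3. In 14.3, keep the grade and attribution of an open related SAE, and any related death, reportable past transplant, in line with 8.4.
4. In 12.3, state that every dosed patient stays in the safety analysis whether or not replaced for efficacy.

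The cost is a few sentences and, since deaths and SAE outcomes are already sought after removal, little or no new data collection. The downside is that stopping becomes slightly more likely if early transplants are counted.
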